#### ***Disease Assessments***

- All patients: mSWAT at screening, pre-IFN-gamma lead-in, C1D1, C2D1, then every other cycle thereafter, and for CR/PR, PD or EOT, and in the event of a Skin Flare Reaction.
- Presence of extracutaneous disease at enrollment: Sezary flow at pre-IFN-gamma lead-in, C2, C6, C10, then every 4 cycles and in the event of a Skin Flare Reaction; Imaging at screening, C5-6, C9-10, (before MK-3475 (pembrolizumab) is administered at cycle 6, and 10) then every 4 cycles, both Sezary flow and imaging are performed to confirm PR and/or CR, when suspect PD and at EOT.
- Absent extracutaneous disease at enrollment: Imaging at screening, Sezary flow at pre-IFN-gamma lead-in, then both are performed to confirm PR and/or CR, when suspect PD, at EOT and in the event of a Skin Flare Reaction.

#### **5.1.1.1 *MK-3475 (pembrolizumab)***

Trial treatment of MK-3475 (pembrolizumab) will be administered on Day 1 of each 3-week treatment cycle after all procedures/assessments have been completed. Trial treatment may be administered up to 7 days before or after the scheduled Day 1 of each cycle due to administrative reasons, beginning with Cycle 2. A 3-day window is allowed for Cycle 1.

**Note:** Dosing interruptions are permitted in the case of medical / surgical events or logistical reasons (*i.e.*, elective surgery, unrelated medical events, patient vacation, holidays) not related to study therapy. Patients should be placed back on study therapy within 3 weeks of the scheduled interruption. The reason for interruption should be documented in the patient's study record.

MK-3475 (pembrolizumab) will be administered as a dose of 200 mg using a 30-minute IV infusion. Infusion timing should be as close to 30 minutes as possible; however, a window of -5 minutes and +10 minutes is permitted (*i.e.*, infusion time is 25 – 40 minutes).

#### **5.1.1.2 *Interferon-gamma (Actimmune)***

IFN-gamma will be administered subcutaneously per the approved package insert instructions, self-administered by the patient whenever possible. The optimum sites of subcutaneous injection are the abdomen, right and left deltoid and anterior thigh. Appropriate counseling in the administration of subcutaneous injections must occur

before patients are allowed to self-administer IFN-gamma. If the patient is unable to self-administer, a family member or caregiver may administer IFN-gamma to the patient after proper counseling in the administration of subcutaneous injections. Dosages will be increased for inadequate response as described above and will be decreased for toxicities as described above. Since toxicities may be constitutional in nature, investigator discretion will be necessary to determine the appropriate dose, the goal being to find a tolerable dose to keep patients on study.

### 5.1.2 Synovial Sarcoma

Regimen Description (Treatment Group 2)				
Agent	Premedications; Precautions	Dose	Route	Schedule
MK-3475 (pembrolizumab)	None	Patients ≥18 years of age: 200 mg  Patients <18 years of age: 2 mg/kg (max= 200 mg)	Intravenous	Every three weeks starting on Day 1 of Cycle 1, followed by Day 1 of each 3-week cycle.
Interferon-gamma- 1b	Antihistamines, analgesics, nonsteroidal anti-inflammatory drugs (NSAIDs), anti- depressants.	100 mcg/m 	Subcutaneous	Once per week starting one week prior to the first dose of MK-3475 (pembrolizumab).

#### 5.1.2.1 *MK-3475 (pembrolizumab)*

MK-3475 (pembrolizumab) will be administered on Day 1 of each 3-week cycle after all procedures/assessments have been completed. MK-3475 (pembrolizumab) may be administered up to 7 days before or after the scheduled Day 1 of each cycle, if needed due to logistical reasons, beginning with Cycle 2. A 3 day window is allowed for Cycle 1.

Note: Dosing interruptions are permitted in the case of medical/surgical events or logistical reasons (e.g., elective surgery, unrelated medical event, patient vacations or holidays) not related to study therapy. Patients should be placed back on study therapy within 3 weeks of the scheduled interruption. The reason for interruption should be documented in the patient's study record.

In patients ≥18 years of age, MK-3475 (pembrolizumab) will be administered at a fixed dose of 200 mg using a 30-minute IV infusion.

In patients <18 years of age, MK-3475 (pembrolizumab) will be administered at a dose of 2 mg/kg (max=200 mg) using a 30-minute IV infusion.

Infusion timing should be as close to 30 minutes as possible. However, a window of -5 minutes and +10 minutes is permitted (i.e., infusion time is 25-40 minutes).

#### 5.1.2.2 *Interferon Gamma-1b (ACTIMMUNE®)*

Interferon gamma-1b will be administered at a dose of 100 mcg/m^2 once per week, starting one week prior to initiating pembrolizumab. Interferon gamma-1b will be administered subcutaneously per the approved package insert instructions, self-administered by the patient whenever possible. If the patient is unable to self-administer, a family member or caregiver may administer interferon gamma-1b to the patient. Appropriate counseling in the administration of subcutaneous injections must occur prior to the start of treatment. Patients will be given an injection log to record drug self-administration and to make note of toxicities. If substantial toxicity occurs, interferon gamma-1b, but not pembrolizumab, will be dose de-escalated. The dose of interferon gamma-1b will be reduced to for certain Gr 3 toxicities as outlined in [Section 6.1.4](#).

NOTE: For synovial sarcoma patients the dose of interferon gamma-1b will be reduced by 50 mcg/m^2 (50%). Grade 3 flu-like symptoms including fevers, fatigue, myalgias, or other patient reported symptoms that resolve to grade 1 within 48 hours should not trigger an interferon gamma-1b dose change.

## 5.2 Study Design, Interim Futility, and Safety Evaluation

### 5.2.1 Mycosis Fungoides/Sézary Syndrome (Treatment group 1)

This is a single arm, open label, interventional study to evaluate the efficacy and safety of the combination immunotherapy with MK-3475 (pembrolizumab) and IFN-gamma in Mycosis Fungoides or Sézary Syndrome, stages IB-IV, who have relapsed, progressed or otherwise failed after at least one standard systemic therapy. There is no planned stratification. 30 patients will be enrolled on a continuous basis.

MK-3475 (pembrolizumab) will be a 200-mg flat dose administered intravenously every 3 weeks, remaining unchanged throughout the study.

In this single stage phase II open label trial, we will have an interim futility analysis. When 12 patients have been followed for 6 months, we will perform the interim futility analysis. If ORR is less than 33% (4 or less CR+PR), the trial will stop and we will accept the null that combination therapy is no better than monotherapy. Otherwise, trial will continue until 30 patients accrue. If ORR is at least 57% (17 or more CR+PR) at the final analysis, we will accept the alternative that combination therapy is significantly better than monotherapy.

There is a planned interim safety review after the first 12 patients are enrolled. If 4 or more out of 12 patients experience a study drug related SAE within the first 10 weeks of therapy, the trial will not be allowed to continue further enrollment and treatment unless or until reviewed and approved by the CITN and NCI CTEP.

### 5.2.2 Synovial Sarcoma (Treatment Group 2)

The study is a single arm, open label trial of interferon gamma-1b and MK-3475 (pembrolizumab) for patients with advanced (unresectable or metastatic) synovial sarcoma. Both adult and pediatric patients are eligible to participate in this trial. Patients will receive interferon gamma-1b at a dose of 100 mcg/m^2 weekly, as this dose has been found to be relatively well tolerated and successful at inducing MHC expression and T cell infiltration into synovial sarcoma tumors. Interferon gamma-1b will begin one week prior to initiating MK-3475 (pembrolizumab). MK-3475 (pembrolizumab) will be given at a standard fixed dose of 200 mg administered every 3 weeks. Thus patients will receive one dose of interferon gamma-1b priming their tumors for checkpoint blockade using MK-3475 (pembrolizumab). If substantial toxicity occurs, interferon gamma-1b, but not MK-3475 (pembrolizumab), will be dose de-escalated.

The primary endpoint of the study will be the overall response rate (ORR) based on RECIST v. 1.1. The ORR is defined as the complete response rate (CR) combined with the partial response rate (PR). Based on historical controls, we estimate the ORR of single agent pembrolizumab is less than 5%. Twelve patients will be enrolled initially. If one or more of these patients respond, an additional four patients will be enrolled. If three or more patients respond the treatment will be considered promising.

Toxicity will be assessed by CTCAE v. 5.0. Although interferon gamma-1b in combination with MK-3475 (pembrolizumab) has previously been seen to be safe, its side effect profile has not been confirmed in a synovial sarcoma patient population or in a population of patients with cold tumors. There is no reason to suspect there would be additional toxicity in these patients however, we will adopt CTEP's data safety monitoring plan of every two week teleconferences attended by all participating site principal investigators, CTEP staff and CITN Coordinating Center staff to oversee the safety of the trial. During each activated protocol teleconference all patient toxicities, including all serious adverse events (SAE) and all other clinical data will be reviewed. Any SAE suspected to be attributed to the study regimen will be distributed to all participating site principal investigators and their staff on an urgent basis. If necessary, an ad hoc teleconference may be convened to discuss any adverse event determined to be a patient safety issue or if the adverse event is suspected of being related to study treatment.

Radiographic assessment by CT scan will occur every 12 weeks. Response and progression will be determined using RECIST v1.1. All patients with either a CR, PR or stable disease (SD) will continue therapy for up to two years. Patients will be followed for up to two years after study discontinuation for disease status and survival. Patients with radiographic progression but who are otherwise stable without symptomatic progression may continue treatment up until confirmation at the next radiographic imaging time point in order to assess for possible pseudo progression. ORR based on immune related response criteria (IRRC) will also be noted as an exploratory endpoint.

### **5.3 General Concomitant Medication and Supportive Care Guidelines (Treatment Group 1 and 2)**

#### **5.3.1 MK-3475 (pembrolizumab) Concomitant Medication**

Medications or vaccinations specifically prohibited in the exclusion criteria are not allowed during the ongoing trial. If there is a clinical indication for any medication or vaccination specifically prohibited during the trial, discontinuation from trial therapy or vaccination may be required. The investigator should discuss any questions regarding this with CTEP. The final decision on any supportive therapy or vaccination rests with the investigator and/or the patient's primary physician; however, the decision to continue the patient on trial therapy or vaccination schedule requires the mutual agreement of the Investigator, CTEP, and the patient.

##### **5.3.1.1 *Acceptable Concomitant Medications***

All treatments that the investigator considers necessary for a patient's welfare may be administered at the discretion of the investigator in keeping with the community standards of medical care. All concomitant medication will be recorded on the case report form (CRF) including all prescription, over-the-counter (OTC), herbal supplements, and IV medications and fluids. If changes occur during the trial period, documentation of drug dosage, frequency, route, and date may also be included on the CRF.

All concomitant medications received within 30 days before the first dose of trial treatment and 30 days after the last dose of trial treatment should be recorded. Concomitant medications administered after 30 days after the last dose of trial treatment should be recorded for serious adverse events (SAEs).

##### **5.3.1.2 *Prohibited Concomitant Medications***

Patients are prohibited from receiving the following therapies during the Screening and Treatment Phase (including retreatment for post-complete response relapse) of this trial:

- Antineoplastic systemic chemotherapy or biological therapy.
- Immunotherapy not specified in this protocol.
- Chemotherapy not specified in this protocol.
- Investigational agents other than MK-3475 (pembrolizumab) and Interferon-gamma (Actimmune).
- Radiation therapy

**Note:** Radiation therapy to a symptomatic solitary lesion or to the brain may be considered on an exceptional case by case basis after consultation with CTEP. The patient must have clear measurable disease outside the radiated field. Administration of palliative radiation therapy will be considered clinical progression for the purposes of determining PFS.

- Live vaccines within 30 days before the first dose of trial treatment and while participating in the trial. Examples of live vaccines include, but are not limited

to, the following: measles, mumps, rubella, chicken pox, yellow fever, rabies, *Bacillus Calmette–Guérin (BCG)*, and typhoid (oral) vaccine. Seasonal influenza vaccines for injection are generally killed virus vaccines and are allowed; however, intranasal influenza vaccines (e.g., *Flu-Mist*®) are live attenuated vaccines, and are not allowed.

- Systemic glucocorticoids for any purpose other than to modulate symptoms from an event of suspected immunologic etiology or for physiologic replacement using 10mg/day or less of Prednisone or equivalent. The use of physiologic doses of corticosteroids may be approved after consultation with the study PI and CTEP.
- **NOTE:** For the synovial sarcoma patients in this trial, systemic glucocorticoids used for  $\leq$  10 days for acute inflammatory symptoms (e.g., allergic reaction), or used at a low dose (prednisone  $\leq$  10 mg/day or equivalent) for physiologic replacement may be administered at the discretion of the treating physician.

Patients who, in the assessment by the investigator, require the use of any of the aforementioned treatments for clinical management should be removed from the trial. Patients may receive other medications that the investigator deems to be medically necessary.

The Exclusion Criteria describes other medications which are prohibited in this trial.

There are no prohibited therapies during the Post-Treatment Follow-up Phase.

#### **5.4 Duration of Therapy (Treatment Group 1 and 2)**

In the absence of treatment delays due to AE(s), treatment may continue for up to two years or until 1 of the following criteria applies:

- Disease progression warranting alternative systemic therapy and without evidence of clinical benefit from continued MK-3475 (pembrolizumab) + Interferon-gamma. Patients who continue MK-3475 (pembrolizumab) + Interferon-gamma after initial disease progression will be discontinued from study for any additional disease progression of 25% or more.
- Intercurrent illness that prevents further administration of treatment
- Adverse event(s) which require(s) treatment discontinuation (see also [Section 6](#)):
  - Any dosing interruption lasting  $>12$  weeks with the following exceptions: Dosing interruptions  $>12$  weeks that occur for non-drug-related reasons may be allowed if approved by the Principal Investigator. Before re-initiating treatment in a patient with a dosing interruption lasting  $>12$  weeks, the Principal Investigator must be consulted.
  - Tumor assessments should continue as per protocol even if dosing is interrupted.
- Any patient requiring systemic steroid or other immunosuppressive treatment. (Steroids may be allowed if they can be tapered, see [section 6.1.3](#).)

- Patient decides to withdraw from the study
- General or specific changes in the patient's condition render the patient unacceptable for further treatment in the judgment of the investigator
- Patient noncompliance
- Pregnancy
  - All women of child bearing potential should be instructed to contact the investigator immediately if they suspect they might be pregnant (*e.g.*, missed or late menstrual period) at any time during study participation.
  - The investigator must immediately notify CTEP in the event of a confirmed pregnancy in a patient participating in the study.
- Termination of the study by sponsor
- The drug manufacturer can no longer provide the study agent

The reason(s) for protocol therapy discontinuation, the reason(s) for study removal, and the corresponding dates must be documented in the Case Report Form (CRF).

## **5.5 Duration of Follow-Up (Treatment Group 1 and 2)**

All patients, regardless of reason for discontinuation from study, will be followed for AE/SAE resolution for 30 days after removal from study. All patients will be followed for survival either by in-person visit or by telephone assessment every 12 weeks until 1 year after EOT.

Disease status and overall survival data will be collected and reported every 12 weeks, either by in-person visit or by telephone assessment.

After disease progression or start of new anticancer treatment, patient will be followed for overall survival only. Survival follow-up will continue until death or 1 year after the end of treatment, whichever occurs first.

In subjects who discontinue study therapy without documented disease progression, every effort should be made to continue monitoring their disease status by Olsen assessment (for patients with Mycosis Fungoides) or by CT scan (for patients with synovial sarcoma) every 12 weeks ( $\pm$  7 days) until (1) the start of new anticancer treatment, (2) documented disease progression, (3) death, or (4) the end of the study, whichever occurs first. If a previous assessment was obtained within 4 weeks before the date of discontinuation, then an additional assessment at treatment discontinuation isn't mandatory.

Patients removed from study for unacceptable AE(s) will be followed until resolution or stabilization of AE; in addition the patients will be followed for disease status and overall survival, as described above.

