## **Treatment Group 2**

- 1.2.2 To determine the progression-free survival (PFS) and overall survival (OS) for patients with advanced synovial sarcoma receiving interferon gamma-1b and MK-3475 (pembrolizumab).
- 1.2.3 To determine the tolerability of the combination of interferon gamma-1b and MK-3475 (pembrolizumab) based on CTCAE version 5.0

***Hypotheses:*** The combination of interferon gamma-1b and pembrolizumab will lead to superior PFS and OS. Both RECIST v. 1.1 and the immune related response criterion will be used for this endpoint.

The combination of interferon gamma-1b and MK-3475 (pembrolizumab) will be well tolerated in patients with advanced synovial sarcoma.

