## 2.2 Synovial Sarcoma (Treatment Group 2)

Synovial sarcoma is a rare, translocation-driven, soft-tissue sarcoma (STS) subtype affecting approximately 800 Americans annually, most commonly young adults (typically about 20-30 years of age), but also children and adolescents. These cancers often initially present with localized, curable disease but for about 50% of patients, the median survival is approximately 16 months [[Constantinidou 2013](#)]; [[Ladanyi 2002](#)]; [[Sultan 2009](#)]; [[Kampe 1993](#)]. Synovial sarcoma should be an ideal target disease for immunotherapy as these tumors typically have high expression level of a number of highly-immunogenic, cancer-testis (CT) antigens including NY-ESO-1, MAGE-A4 and PRAME (**Fig. 1**) [[Sultan 2009](#)]. Unlike other cancers that most often have sporadic heterogeneous expression of CT antigens, in synovial sarcoma tumors NY-ESO-1 is expressed in >80% of patients and generally with very strong, homogenous expression throughout the tumor (**Fig. 2**). Despite strong expression of these highly immunogenic proteins, synovial sarcoma has not responded well to anti-programmed death-1 (anti-PD-1)/ anti-programmed death-ligand 1 (anti-PD-L1) targeted therapies. In the SARC28 study, only one of 10 synovial sarcoma patients had a partial response, and no PRs were seen on the Alliance trial using nivolumab [[Tawbi 2016](#)]; [[D'Angelo 2015](#)]. A randomized vaccine trial recently presented at the 2017 ESMO treated 43 patients with single agent atezolizumab and none had a PR [[Chawla 2017](#)].

[figure not shown]

Fig. 1: Heat map illustrating results

from a custom made qPCR array testing for levels of gene expression of 19 Cancer-Testis Antigens. RNA was extracted from frozen, banked well/de-differentiated liposarcomas (MRCL not shown), leiomyosarcomas, undifferentiated pleomorphic sarcomas and synovial sarcoma tumors. Synovial sarcoma tumors had strong expression of NY-ESO-1, MAGE-A4 and PRAME.

[figure not shown]

Fig. 2: Immunohistochemistry testing for NY-ESO-1 expression in a synovial sarcoma patient treated at the Seattle Cancer Care Alliance. This staining illustrates the classic homogenous staining pattern

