### Summary Analysis Strategy for Efficacy Endpoints

Endpoint/Variable	Statistical Method	Analysis Population	Missing Data Approach
Primary:			
Overall Response Rate (ORR)	Binomial proportion	Evaluable population as defined	Subjects without any efficacy evaluation will be excluded; if one compartment is missing data, that compartment will be considered non-response.
Secondary:			
Progression-free survival (PFS)	Kaplan-Meier method	All efficacy or safety evaluable patients	Censored at last follow-up or start of new significant therapy
Overall survival (OS)	Kaplan-Meier method	All efficacy or safety evaluable patients	Event is death due to any cause, otherwise it is considered censored at last follow-up
Tolerability	Binomial proportion	All enrolled patients	All AEs and SAEs will be summarized

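### Group 2 survival follow-up is counted from end of treatment, so patients who fail earliest are followed for the shortest time and late overall survival may be overstated; the size depends on an unresolved conflict between sections 5.2.2 and 5.5

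*Combined protocol and SAP*

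**What the plan says.** Objective 1.2.2 makes OS a secondary endpoint for Group 2, and the hypothesis beneath it reads "The combination of interferon gamma-1b and pembrolizumab will lead to superior PFS and OS". No comparator value is given. The Group 2 efficacy table in 13.2.1 specifies Kaplan-Meier for OS: "Event is death due to any cause, otherwise it is considered censored at last follow-up". It sets no truncation time and no common cutoff.

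The length of follow-up is stated in two ways. Section 5.5, headed for both treatment groups, says "Survival follow-up will continue until death or 1 year after the end of treatment, whichever occurs first" and gives the same one-year limit in its opening paragraph. Section 5.2.2, which concerns Group 2 only, says "Patients will be followed for up to two years after study discontinuation for disease status and survival". The Group 2 calendar in 10.2 lists survival contact every 12 weeks (plus or minus one) without an end date.

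On time on treatment, 5.2.2 says "All patients with either a CR, PR or stable disease (SD) will continue therapy for up to two years", with CT every 12 weeks. Section 5.8.2 lets clinically stable patients with radiographic progression stay on treatment until confirmation imaging 6 to 12 weeks later. Section 5.4 lists other reasons for stopping, several of which can apply before the first scan. The only survival benchmark is in the background, section 2.2: "for about 50% of patients, the median survival is approximately 16 months".

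**The concern.** Kaplan-Meier is unbiased when patients censored at a given time have the same outlook as those still followed. Here the censoring time is the end of treatment plus a fixed window. Patients who progress or decline early leave the risk set first, and the later part of the curve rests on those who stayed on treatment. If early failures also die sooner, the late curve is too high. Changing the window from one year to two shrinks the effect but leaves its cause, because either window starts when treatment or study participation stops.

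Group 2 has at most 16 patients and no control arm, so OS can only be read against history. A tail that rests on a few patients selected by time on treatment could be mistaken for benefit of the combination.

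**Working it through.** **Plan's own figures.** The plan gives no OS event count, precision or power. Its only Group 2 efficacy design figures concern response. With 12 patients first, a stop at 0 responses and success at 3 or more of 16, the success probability is the sum over x = 1 to 12 of Bin(x; 12, p) × P(Bin(4, p) ≥ 3 − x). This gives 0.0427 at p = 0.05 and 0.8013 at p = 0.25. Early stopping is 0.540 and 0.032. All match 13.2.2 (4.3%, 80.1%, 54%, 3%). None depends on OS.

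**Length of follow-up.** Months = weeks × 7 / 30.4375. Potential follow-up = end of treatment + 12 months (5.5) or + 24 months (5.2.2, taking study discontinuation as end of treatment).

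| End of treatment | Months | Followed to, 5.5 | Followed to, 5.2.2 |
|---|---|---|---|
| Week 3 (assumed early stop) | 0.69 | 12.7 | 24.7 |
| Week-12 scan | 2.76 | 14.8 | 26.8 |
| Week-12 progression, confirmed week 18 | 4.14 | 16.1 | 28.1 |
| Week-12 progression, confirmed week 24 | 5.52 | 17.5 | 29.5 |
| Two full years | 24.0 | 36.0 | 48.0 |

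Counting the one-week interferon lead-in moves the week-12 row under 5.5 to 15.0 months.

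**Size of the bias.** The documents give no progression-free survival (PFS) median and no link between PFS and later survival, so these are assumptions:

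- PFS exponential with median 2.8, 4 or 6 months.
- Post-progression survival exponential, linked to PFS by a Gaussian copula with correlation 0, 0.3 or 0.5, and scaled so that median OS is 16 months (the section 2.2 figure).
- Treatment ends at the first 12-weekly scan at or after progression, or 12 weeks later, and at 24 months at the latest.
- 400,000 simulated patients per scenario; nine scenarios per rule; counts scaled to 16 patients.

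| Rule | Excess at 24 months (points) | Excess at 30 months (points) |
|---|---|---|
| 5.5, stop at progression scan | about 1 to 8 | about 1 to 13 |
| 5.5, all treated to 12-week confirmation | under 0.5 to about 4 | under 1 to about 8 |
| 5.2.2, stop at progression scan | nil | at most about 0.7 |

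In the middle scenario (PFS median 4 months, correlation 0.3, 5.5, stop at the scan), true OS at 24 months is 0.318 and Kaplan-Meier gives 0.361, an excess of 0.361 − 0.318 = 0.043. At 30 months the values are 0.223 and 0.293, an excess of 0.070.

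Across the nine scenarios of the first row:

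- About 3 to 7 of 16 patients are censored alive before month 24.
- About 1 to 4 (0.6 to 3.5) remain at risk at month 24, when about 5 are truly alive.
- Deaths are observed in 53 to 70% of patients, against 82 to 89% with complete follow-up to month 36.
- The Kaplan-Meier median is overstated by less than half a month.

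A different model (median time to progression 3 or 6 months; post-progression hazard either equal for all, or twice as high after progression by the first scan) also gave upward bias under 5.5 with a stop at the scan. The excess was 0.9 to 4.0 points at 24 months and 1.6 to 4.7 at 30, with a median of 16.05 to 16.4 months.

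**The case against.** The strongest objection is that the one-year rule is not settled for Group 2. Section 5.2.2 is the more specific text, and under it a patient stopped at the first scan is followed to about 26.8 months with negligible bias. This stands: the larger figures apply only if 5.5 governs. It does not dispose of the point, because 5.5 is the dedicated follow-up section, it states the one-year limit twice, and the words "up to" in 5.2.2 can be read as a ceiling.

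A reader might infer that the earliest failures are all censored at about month 15, just before the protocol's own median, and that the curve is sound until then. The documents do not support this. Treatment to confirmation moves the time to 16.1 to 17.5 months, while stops before week 12 under 5.4 bring it to about 12 to 13. Month 15 is neither a common censoring time nor a floor. The 16-month figure is background with no stated time origin. Trial patients have had at least one prior line of chemotherapy, and myxoid/round cell liposarcoma is also eligible, so it is only a rough benchmark.

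It is also fair that the upper figures rest on assumed inputs, and that sampling error is large. Even with complete follow-up of 16 patients, the standard error at 24 months is √(0.318 × 0.682 / 16) = 11.6 points, and at 30 months √(0.223 × 0.777 / 16) = 10.4 points. The plan names no 24- or 30-month OS estimate. These facts limit the consequence. They do not make censoring independent of outcome, and the confirmation allowance favours clinically stable patients, which tightens the link between follow-up and prognosis.

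**Conclusion.** The concern holds in a limited form. Survival follow-up tied to end of treatment gives the shortest follow-up to the patients who fail first, and Kaplan-Meier with censoring at last follow-up does not correct for that. Under 5.5 and the stated assumptions, late OS is overstated by about 1 to 8 points at 24 months and 1 to 13 at 30. If all are treated to a 12-week confirmation, the excess is at most about 4 and 8 points. The direction was upward in every one-year scenario, including those with post-progression survival independent of PFS. Under 5.2.2 the problem is close to nil over the same period.

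A reader might go further and conclude that median OS or the trial's efficacy decision is compromised. Neither follows: the median moves by less than half a month, and the treatment is called promising on response rate alone. The weakness affects a descriptive secondary endpoint and is worth correcting because the two sections have to be reconciled in any case.

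**What to change.** Reconcile 5.2.2 and 5.5 into one Group 2 survival follow-up rule that does not depend on when treatment ended. Continue the existing 12-weekly telephone contact for every patient to the same time from first interferon gamma-1b dose or enrolment (for example 36 months from first dose), or to a common data cutoff. State the rule in both sections and add the end date to the 10.2 calendar. Amending 5.5 alone would leave 5.2.2 in conflict. Note that 36 months is the longest follow-up possible under 5.5 but not under 5.2.2, where it is 48; if the longer follow-up is wanted for long-treated patients, the common time should be set accordingly.

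If this is not adopted, say in 13.2.1 that Kaplan-Meier OS is reported only up to the shortest potential follow-up among enrolled patients (under 5.5, 12 months after the earliest end of treatment). A fixed month 15 should not be used, because patients who stop before the first scan are not followed that long.

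The cost is some extra telephone calls for at most 16 patients, mostly those who stop early. The fallback adds no follow-up but gives up the late part of the curve.
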